10.4.1.2 Onset Date, End Date

If an AE starts during the study but did not end before the final closing (follow-up) visit, the Investigator must make a reasonable effort to establish the outcome and the end date of the AE. If this is not possible (e.g., because the AE is still ongoing) or the subject is lost to follow-up, there will be no end date for the AE.

For all AEs that resolve, resolve with sequelae, or have a fatal outcome, an end date must be provided.

If an AE stops and restarts later, all occurrences have to be recorded separately.

If an AE starts as a non-serious AE and becomes serious at a later point in time, the following applies in regard to the onset date:

The onset date of the AE will reflect the first occurrence of signs and/or symptoms associated with the event, or the date the first diagnosis was made, independent of event seriousness at that time.

10.4.1.3 Assessment of Severity

Severity of AEs refers to the extent to which an AE affects the subject’s daily activities. The severity of AEs and toxicities must be graded by the Investigator according to the NCI CTCAE version 4.03. The NCI CTCAE version 4.03 can be found at <http://www.oncology.tv/SymptomManagement/NationalCancerInstituteUpdatesCTCAEto403.aspx>.

Grade 1	Mild; asymptomatic or mild symptoms; clinical or diagnostic observations only; intervention not indicated.
Grade 2	Moderate; minimal, local or noninvasive intervention indicated; limiting age-appropriate instrumental activities of daily living (ADL)*.
Grade 3	Severe or medically significant but not immediately life-threatening; hospitalization or prolongation of hospitalization indicated; disabling; limiting self-care ADL**.
Grade 4	Life-threatening consequences; urgent intervention indicated.
Grade 5	Death related to AE.

*Instrumental ADL refer to preparing meals, shopping for groceries or clothes, using the telephone, managing money, etc.

**Self-care ADL refer to bathing, dressing and undressing, feeding self, using the toilet, taking medications, and not bedridden.

The term “severity” is used to describe the intensity of an AE. This is not the same as “serious”. Seriousness, not the severity, serves as the guide for defining regulatory reporting obligations. Notwithstanding this differentiation, AEs of severity grade 4 or 5 (life-threatening or fatal) will meet the criteria for seriousness and will thus qualify as SAEs/irAEs.

If there is a change in severity of an AE, it will be captured as 1 AE, with the highest severity grade recorded.

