10.4 Safety Variables

10.4.1 Adverse Events

10.4.1.1 Adverse Event Definition

An AE is defined as any untoward medical occurrence in a clinical study subject administered a medicinal product which does not necessarily have a causal relationship with this treatment. An AE can therefore be any unfavorable and unintended sign (including an abnormal laboratory finding), symptom, or disease temporally associated with the use of a medicinal (investigational) product, whether or not it is related to the medicinal (investigational) product. This includes an exacerbation of pre-existing conditions or events, intercurrent illnesses, drug interaction or the significant worsening of the indication under investigation that is not recorded elsewhere in the eCRF under specific efficacy assessments. Anticipated fluctuations of pre-existing conditions, including the disease under study that do not represent a clinically significant exacerbation or worsening need not be considered AEs.

The Investigator will monitor each subject for clinical and laboratory evidence of AEs on a routine basis throughout the study. Should an Investigator become aware of any study drug-related SAEs following this period these must also be reported as stated in [Section 10.4.4.3](#). Adverse event monitoring starts from the time the subject consents to the study until they complete the trial. All reportable AEs will be followed to a satisfactory conclusion. Any reportable drug-related AEs that are unresolved at the follow-up visit are to be followed up by the Investigator until resolution or stabilization.

AEs will be elicited by asking the subject a non-leading question, for example, “Have you experienced any new or changed symptoms since we last asked/since your last visit?” AEs should be reported on the appropriate page of the eCRF.

Each separate AE episode must be recorded. For example, if an AE resolves completely or resolves to baseline and then recurs or worsens again, this must be recorded as a separate AE. For AEs to be considered intermittent, the events must be of similar nature and severity.

Tumor progression is not an AE. However, the medical conditions associated with disease progression must be documented as AE.

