10.4.2 Immune-Related Adverse Events

An irAE, will be considered as a subset of AEs defined as a clinically significant AE of any organ that is associated with study drug exposure, of unknown etiology, and is consistent with an immune-mediated mechanism. Serologic, immunologic, and histologic (biopsy) data may be used to support an irAE diagnosis. Appropriate efforts should be made to rule out neoplastic, infectious, metabolic, toxic, or other etiologic causes of the irAE.

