10.4.4 Serious Adverse Events

10.4.4.1 Serious Adverse Event Definition

A SAE is any AE, regardless of dose, causality or expectedness, that:

- **Results in death:** Death is an outcome of an AE and not an AE in itself.
- **Is life-threatening:** This refers to an event in which the subject was at risk of death at the time of the event. It does not refer to an event, which hypothetically might have caused death, if it were more severe.
- **Requires inpatient hospitalization or prolongs existing inpatient hospitalization:** In general, hospitalization signifies that the subject has been admitted (usually involving at least an overnight stay) at the hospital or emergency ward for observation and/or treatment that would not have been appropriate in the physician's office or outpatient setting. Complications that occur during hospitalization are AEs. If a complication prolongs hospitalization or fulfils any other serious criteria, the event is serious. When in doubt as to whether hospitalization occurred or was necessary, the AE should be considered serious. Note: Elective admissions to hospital for subject convenience or for planned procedures or investigations or treatment as specified in this protocol are not SAEs, and do not require SAE reporting. However, if the underlying condition for which hospital treatment or surgery had been planned worsened during the study, the worsening of the condition is to be reported as an SAE.
- **Results in persistent or significant incapacity or disability:** This means a substantial disruption of a person's ability to conduct normal life functions. It does not include experiences of relatively minor medical significance or accidental trauma (e.g., sprained ankle), which do not constitute a substantial disruption.
- **Is a congenital anomaly or birth defect**
- **Is any other medically important event:** Defined as an event that may jeopardize the subject or may require intervention to prevent 1 of the outcomes listed above. Medical and scientific judgement must be exercised in deciding whether an event is serious. Any new primary cancer must be reported as an SAE.

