10.4.4.2 Adverse Events not considered serious

The following events do not meet the criteria for SAEs and will therefore not be reported as an SAE:

- Any planned hospitalization before inclusion in the study.
- Admission for elective treatment of a condition unrelated to the studied indication or its treatment.
- Admission as a part of the normal planned treatment or monitoring of the studied indication and not associated with any deterioration in condition.
- Admission for social reasons, without an underlying medical condition, including hospice.
- Disease progression and events which are unequivocally related to disease progression regardless of their outcome and regardless whether they otherwise would fulfil seriousness criteria.

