10.4.4.3 Reporting of Serious Adverse Events

SAEs must be reported from signing the informed consent up to and including 30 respectively 60 days after administration of the last dose, whether or not considered to be related to the investigational product.

Any SAE must be reported by the Investigator on a SAE Reporting Form **within 24 hours** of Investigator's awareness to **INC Research Safety & Pharmacovigilance**:

Email: ^{PPD} [REDACTED]

Fax: ^{PPD} [REDACTED]

The 4 minimum criteria for a valid SAE report include:

- Site identifier
- Subject identifier
- Event term
- Study drug

The Investigator should not wait to receive additional information to document fully the event before notification of a SAE. As soon as the 4 minimum mentioned above criteria are fulfilled, the Investigator must report the SAE within 24h of awareness. In addition, all further information requested on the SAE Reporting Form should be completed and sent to INC Research Safety & Pharmacovigilance as soon as possible. If the SAE has not been reported within the specified timeframe, a reason for delay must be provided when sending the SAE Reporting Form.

Where applicable, information from relevant laboratory results, hospital case records, and autopsy reports should be obtained and reported to INC Research Safety & Pharmacovigilance as soon as possible as well.

Instances of death, congenital abnormality, or an event that is of such clinical concern as to influence the overall assessment of safety, if brought to the attention of the Investigator at any time after cessation of study drug administration and linked by the Investigator to this study, should be reported to the study monitor.

Any laboratory values considered clinically significant or meeting grade 4 (NCI CTCAE) or above should be considered AEs and should be captured in the eCRF. Any events reported that also meet the SAE criteria should be reported in line with SAE reporting requirements.

All SAEs reported to INC Research Safety & Pharmacovigilance will be processed according to internal standard operating procedures (SOPs). INC Research Safety & Pharmacovigilance may request additional information for any SAE as judged necessary.

Any SAE occurring at any time after completion of study treatment or after the designated follow-up period that the Investigator consider to be related to any study drug must be reported to the Sponsor/INC Research.

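### The rule in 10.4.1.3 that every grade 4-5 AE is an SAE/irAE conflicts with the irAE definition in 10.4.2 and, lacking a cross-reference, with the progression exemption in 10.4.4.2

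*Combined protocol and SAP*

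**What the plan says.** - **10.4.1.3 (Assessment of Severity)** separates severity from seriousness and then expressly sets that separation aside for the top two grades: "AEs of severity grade 4 or 5 (life-threatening or fatal) will meet the criteria for seriousness and will thus qualify as SAEs/irAEs". It states no exception and refers to no other section.
- **10.4.2 (Immune-Related Adverse Events)** treats irAEs as a subset of AEs that must be clinically significant and "associated with study drug exposure, of unknown etiology, and is consistent with an immune-mediated mechanism". It also asks for efforts to exclude other causes, including neoplastic and infectious ones. CTCAE grade is not a criterion.
- **10.4.1.1 (Adverse Event Definition)** says that progression itself is not an AE, but that "the medical conditions associated with disease progression must be documented as AE".
- **10.4.4.2 (Adverse Events not considered serious)** lists among the events that are not SAEs: "Disease progression and events which are unequivocally related to disease progression regardless of their outcome and regardless whether they otherwise would fulfil seriousness criteria".
- **7.2 (Endpoints)** makes SAE occurrence a primary endpoint. **11.1.6 (Safety Variables)** summarizes SAEs and irAEs separately. **10.4.4.3** requires SAEs to be reported within 24 hours of the investigator's awareness.

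**The concern.** One sentence in the severity section assigns two classifications, SAE and irAE, on grade alone, while the sections that define those classes use other criteria. A site that follows 10.4.1.3 to the letter would label a progression-related death as both an SAE and an irAE. A site that follows 10.4.4.2 and 10.4.2 would label it neither.

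The SAE label matters because it feeds a primary endpoint and the expedited reporting stream. The irAE label matters because immune-related toxicity heads the list of anticipated risks in section 6.6 for this first-in-human, immune-activating product. An irAE table that contains unrelated or progression-driven grade 4-5 events would be hard to interpret.

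**Working it through.** The plan states no figure on this point, so there is none to reproduce. The check sets the sections against three kinds of event.

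| Event | 10.4.1.3, read literally | Defining section | Conflict? |
|---|---|---|---|
| Grade 4-5 AE unequivocally due to progression (an AE under 10.4.1.1) | SAE and irAE | Not an SAE (10.4.4.2); not an irAE, since the cause is neoplastic (10.4.2) | Yes, on both labels |
| Grade 4-5 AE unrelated to study drug and to progression | SAE and irAE | Not an irAE (10.4.2) | Yes, on the irAE label |
| Grade 4 laboratory value | SAE and irAE | AE, and an SAE if the criteria are met (10.4.4.3); an irAE only if 10.4.2 is met | irAE label only; no SAE conflict shown |

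**Progression.** The steps are: condition associated with progression, then AE (10.4.1.1), then grade 4 or 5, then SAE (10.4.1.3). Section 10.4.4.2 stops the same event from being an SAE even where it would otherwise fulfil the seriousness criteria. That phrase points to the exemption prevailing. However, 10.4.1.3 does not stop at saying that the criteria are met; it goes on to say that the event qualifies as an SAE, and it does not mention 10.4.4.2.

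**irAE.** The route in 10.4.1.3 is grade alone. The route in 10.4.2 is drug association plus mechanism, with other causes investigated. An event can satisfy the first without the second.

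**Dose escalation.** The DLT definition in 8.4.7 uses relatedness, CTCAE grade and duration, not seriousness. Its irAE exclusion covers only grade 3 irAEs that resolve to grade 1 or less within 7 days. Calling a grade 4 or 5 event an irAE therefore does not remove it from the DLT count, and the 3+3 rules in 8.1.1 are unaffected.

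**Illustrative size.** Take one subject whose only SAE is an event classed differently by the two sections. The shift in the subject-level rate is 1/n. Group sizes are from 8.1.1 and 11.2.2; intervals are exact (Clopper-Pearson) 95%.

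- n = 3: 0/3 = 0% (0 to 70.8%) becomes 1/3 = 33.3% (0.8 to 90.6%)
- n = 6: 0/6 = 0% (0 to 45.9%) becomes 1/6 = 16.7% (0.4 to 64.1%)
- n = 15: 0/15 = 0% (0 to 21.8%) becomes 1/15 = 6.7% (0.2 to 31.9%)
- n = 60: the shift is 1/60 = 1.7 points

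The irAE rate would move by the same 1/n for a subject whose only irAE label came from 10.4.1.3.

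**The case against.** The strongest defence is that the progression conflict is already settled. Section 10.4.4.2 expressly overrides the seriousness criteria, so it can be read as a specific exception to a general rule. The irAE wording can be read as loose drafting, since 10.4.2 gives a full definition. SAEs also go to one central safety group, which could harmonize classifications. Much of this stands: the likely intent is clear, and divergence between sites is a possibility that the documents do not demonstrate. What remains is that 10.4.1.3 is unqualified and a site following it literally would be complying with the protocol.

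A reader might infer three stronger points that the documents do not support.

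- **That grade 4 laboratory values are treated inconsistently.** Section 10.4.4.3 says "Any events reported that also meet the SAE criteria should be reported in line with SAE reporting requirements", which might seem to imply that some grade 4 values are not serious. But that provision also covers clinically significant values below grade 4, so the condition has meaning even if every grade 4 value is serious. Calling a value an AE does not deny that it is an SAE.
- **That seriousness requires actual risk of death.** The limit "It does not refer to an event, which hypothetically might have caused death, if it were more severe" belongs to the life-threatening criterion alone, one of six alternatives in 10.4.4.1. A grade 4 event can be serious by another route, such as hospitalization or medical importance. Outside progression, a grade 5 event meets the death criterion in any case.
- **That 10.4.1.3 contradicts itself.** It acknowledges the severity/seriousness distinction and deliberately departs from it. Section 10.4.4.1 does say "Medical and scientific judgement must be exercised in deciding whether an event is serious", but replacing an automatic rule with investigator judgement is a trade-off that could itself increase variation between sites.

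**Conclusion.** The point holds in two respects. Under 10.4.1.3 as written, every grade 4-5 AE is an irAE, contrary to 10.4.2. It also makes grade 4-5 AEs due to progression SAEs, contrary to 10.4.4.2, whose exemption probably governs but is not referred to. The consequences are confined to the SAE primary endpoint, the irAE summary (not a primary endpoint) and the set of events sent for 24-hour reporting. DLT and 3+3 decisions do not change.

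No expected size can be given. The documents state no frequency for such events, and the number of scheduled blood draws supplies no probability of a grade 4 value. The shifts of 33 and 17 points assume exactly one reclassified subject with no other qualifying event, in a cohort of 3 or 6; any single event has that effect at those sizes. Grade 4-5 events remain visible in the AE summaries by CTCAE grade whatever their seriousness label. This is a correction worth making because the text is wrong as written, not because a large distortion has been shown.

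**What to change.** 1. In 10.4.1.3, delete the reference to irAEs from the grade 4-5 sentence and state that irAE status is assigned only under 10.4.2.
2. In the same sentence, add an exception: *except events covered by 10.4.4.2*.
3. Leave the automatic seriousness rule in place for other grade 4 events, including laboratory values, if the sponsor wants it. A cross-reference to it in 10.4.4.3 would make the two sections consistent.

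No new output is needed for progression-related deaths: 11.1.6 already lists and summarizes deaths due to the study disease by dose level and group.

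The cost is a few words in the protocol and matching wording in the eCRF completion guidance. No assessment, visit, sample size or analysis method changes.

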10.4.1.4 Assessment of Causality

A medically qualified individual (Investigator or his designee) must assess the “relationship” of an AE to RGT100-PEI. The assessment of causality is made using the following categories:

Unrelated:	Clinical event with an incompatible time relationship to study drug administration, and that could be explained by underlying disease or other drugs or chemicals or is incontrovertibly not related to the study drug.
Possible:	Clinical event with a reasonable time relationship to study drug administration, but that could also be explained by concurrent disease or other drugs or chemicals.
Related:	Clinical event with plausible time relationship to study drug administration, and that cannot be explained by concurrent disease or other drugs or chemicals.

The Investigator must endeavor to obtain sufficient information to confirm the causality of the AE (i.e., relation to surgery, study drug, background treatment, other illness, progressive malignancy etc.) and give their opinion of the causal relationship between each AE and study drug. This may require instituting supplementary investigations of significant AEs based on their clinical judgement of the likely causative factors and/or include seeking a further specialist opinion.

Refer to the IB⁴ for all nonclinical safety details relating to RGT100-PEI. A copy of the current approved version of the IB must be held in the Site File for reference. Any change or update to the IB during the trial will be made via substantial amendment.

10.4.1.5 Action Taken as a Result of Adverse Event

The action taken as a result of the AE will be documented in the appropriate section of the eCRF as follows:

- None
- Study drug stopped
- Study drug temporarily interrupted
- Concomitant medication changed, stopped
- Medication to treat AE
- Other, specify

10.4.1.6 Outcome of Adverse Event

The final outcome of the AE will be documented in the appropriate section of the eCRF as follows:

- Recovered
- Recovered With Sequelae
- Not Recovered
- Ongoing
- Unknown
- Death

10.4.1.7 Follow-up of Adverse Events

Adverse events should be followed to determine the outcome.

AEs that are serious or considered related or possibly related to study drug or study procedure must be followed up until the event is resolved, resolved with sequelae or until, in the opinion of the Investigator, the event is stabilized, has been fully assessed and does not require further follow-up or determined to be chronic. Details of AE resolution must be documented in the eCRF.

For all SAEs, where important or relevant information is missing, active follow-up should be undertaken.

All other AEs must be followed up by the Investigator until the AE is resolved, resolved with sequelae or the end of the period of observation (= last study visit), whichever comes first.

Subjects should be followed up for 30 days (or 60 days for subject who have not progressed at Day 30) after receiving the last dose of study drug, and any AEs that occur during this time should be reported according to the procedures outlined above. If AEs that are serious and considered related or possibly related to study drug or study procedure are ongoing at the time of subject's last study visit, all attempts should be made to receive the final outcome.

A follow-up report must be completed when an SAE resolves, is unlikely to change, or when additional information becomes available. In case the SAE is a suspected unexpected serious adverse reaction (SUSAR) follow-up information must be provided within the timelines as requested by the INC Research Safety & Pharmacovigilance.

If new or amended information on a reported SAE becomes available, the Investigator can report this on a new SAE form using the completion guidelines. If using the original form to notify further information, all new or amended information need to be initialed and dated in order all changes are clearly identified.

10.4.1.8 Documentation and Reporting of Adverse Events

AEs should be reported and documented in accordance with the procedures outlined below. All AEs occurring during the study must be documented on the relevant eCRF pages. The following data should be documented for each AE:

- Diagnosis or if not available symptoms
- Classification of 'serious' or 'not serious'
- Severity
- Date of first occurrence and date of resolution (if applicable)
- Action taken
- Causal relationship
- Outcome of event

10.4.2 Immune-Related Adverse Events

An irAE, will be considered as a subset of AEs defined as a clinically significant AE of any organ that is associated with study drug exposure, of unknown etiology, and is consistent with an immune-mediated mechanism. Serologic, immunologic, and histologic (biopsy) data may be used to support an irAE diagnosis. Appropriate efforts should be made to rule out neoplastic, infectious, metabolic, toxic, or other etiologic causes of the irAE.

